trial	therapeutic potential of real-time functional MRI-based (fMRI)				
	neurofeedback tackling self-blaming emotions in patients with major				
	depression who have only had a partial response to standard treatments.				
Primary objective	This study aims at testing clinical benefits and feasibility of a novel fMRI				
	neurofeedback protocol aimed at self-blame-selective neural coupling				
	abnormalities in major depressive disorder.				
Secondary	This study will further aim at investigating neurocognitive mechanisms				
objective (s)	underpinning the remission of depressive symptoms.				
Trial design	Small randomised controlled clinical proof-of-concept trial.				
Outcome measures	Primary outcome measure:				
	1) Reduction of depressive symptoms between Visit 1 and 5 as assessed				
	by the Beck Depressive Inventory (BDI-II). (Reduction of				
	depressive symptoms between Visit 1 and the last treatment session				
	as assessed by the Beck Depressive Inventory (BDI-II) for those who				
	do not complete the study.)				
	Secondary outcome measures:				
	2) Reduction of depressive symptoms between Visit 1 and 5 as assessed				
	by the Montgomery–Asberg Depression Rating Scale (MADRS) by				
	a rater who is blinded to the treatment arm.				
	3) Reduction of self-rated depressive symptoms between Visit 1 and 5				
	as assessed by the Quick Inventory of Depressive Symptomatology				
	(QIDS-SR 16).				
	4) Clinical Global Impression scale change between Visit I and 5 by a				
	rater who is blinded to the treatment arm.				
	5) Withdrawal rates and adverse events after first treatment session.				
	6) Decrease in post vs. pre-training right ATL-SSCR correlation on				
	tMRI (measured by regression coefficients for the time series as				
	extracted by the FRIEND software for self-blame relative to blaming				
	otners (in neuroreedback arm).				
	/) Reductions in implicit self-blaming bias (self-contempt bias BIAT)				
	Detween visit I and 5.				
	Visit 5.				
	9) Positive Affect score increase and Negative Affect score decrease				
	(PANAS scale) between Visit 1 and Visit 5.				
	10) Profile of Mood States (POMS) depression score change between				
	Visit 1 and 5.				
	11) Self-blame ratings obtained prior to the first and after the last				
	treatment session.				

	
 
12) Reductions in agency-incongruent self-blame on short version of the value-related moral sentiment task between Visit 1 and 5.
 
13) Dysfunctional Attitudes Scale (prior & post mood induction if time permits) between Visit 1 and 5.
 
14) Self- & observer rated clinical global impression on Visit 5 for change since Visit 1. (We may have to drop some of the secondary outcome measures depending on time constraints.)
 

Sample size	60  MDD patients completing the first treatment visit after being randomised to one of the two treatment arms (n=24 in each arm, plus an estimated 12 lost
	to follow-up) )
Main eligibility	Main inclusion criteria: DSM-V recurrent major depressive disorder MDD
criteria	with at least one major depressive episode (MDE) of at least 2 months
	duration, insufficiently remitted from a major depressive episode (MDE) for
	at least 6 weeks, so that they display symptoms that are significantly
	bothering or impairing (Psychiatric Status Rating of 3 - 5 over the past 2
	weeks on Longitudinal Interval Follow-up Interview [LIFE]). If treated with
	antidepressants, on stable dose for at least 6 weeks prior participation and
	planning to stay on this dose for the duration of the study. Patients have
	insufficiently responded to at least one course of cognitive behavioural
	therapy (CBT) or antidepressants or are not amenable to these standard
	treatments and are not currently undergoing psychotherapy. Age: 18 or older.
	Right-handedness in order to ensure homogenous response to our right
	hemisphere treatment target. Proficiency in English in order to ensure
	reliable responses on newly developed secondary outcome measures.
	Main exclusion criteria: greater than low suicide risk or risk of violence,
	other current or relevant past DSM-V axis-I psychiatric disorders. MRI
	exclusion criteria.

## **Synopsis Study 2**

#### Trial Design: Case-control observational

In study 2 (case-control study): Panic disorder patients with insufficient remission (n = 30, including 5 dropouts). Healthy controls with no personal or family history of mood, anxiety disorders or schizophrenia (n=30, including 5 dropouts), melancholic MDD (n=30, including 5 dropouts), MDD with no specifiers (n=30, including 5 dropouts).

MDD participants will be either specifically recruited for this study or their data will derive from participation in study 1.

## 1. Background & Rationale

#### **1.1. Need for research in this area**

Depression is a leading cause of disability as measured by years lived with disability (World Health Organization, 2008). This is mainly because individuals with previous episodes of major depression, especially those with residual symptoms, have a greatly increased risk of developing further episodes (Eaton et al., 2008). Even optimal pharmacological and psychotherapeutic treatments fail to prevent recurrence in most patients with major depressive disorder (MDD): meta-analyses show that antidepressant medications (Viguera et al., 1998) and psychotherapy (Piet & Hougaard, 2011) are able to reduce recurrence rates by 50% in the short-term. However, after 5 years, over 60% of patients will have experienced recurrences despite continuing medication (Viguera et al., 1998) or psychotherapy (Bockting et al., 2009). Further, there is no evidence that combining medication and psychotherapy improves long-term outcomes (Lampe et al., 2013) and a high proportion of patients are not amenable to either treatment option (Prins et al., 2009). Therefore, there is an urgent need to develop novel treatments that improve the long-term outcomes of MDD.

#### **1.2. Overall aim of this project**

The overall purpose of this project is to test the therapeutic potential and feasibility of realtime functional MRI-based (fMRI) neurofeedback aimed at self-blaming emotional biases in MDD. Further, we aim at understanding the mechanisms by which self-blaming emotional biases affect treatment outcomes in major depressive disorder. Study 1 aims at testing the clinical benefits and general feasibility of a novel fMRI neurofeedback protocol to tackle selfblame-selective neural coupling abnormalities between the right superior anterior temporal lobe (ATL) and the septal/subgenual cingulate region (SSCR) in major depressive disorder. Study 2 aims at investigating neurocognitive mechanisms underpinning (the remission of) depressive symptoms.

#### 1.3. Thematic background of the proposed work

In an fMRI study, we have identified the neural basis of self-blaming emotional bias in major depressive disorder, which persists after remission of symptoms (Green et al., 2012). More specifically, we detected neural coupling abnormalities between the right superior anterior temporal lobe (ATL) with the septal/subgenual cingulate cortex region (SSCR). Whilst decreased coupling was found in the anterior part of the SSCR during the experience of self-blame compared to other-blame, new data from a recently completed MRC-funded prospective study revealed that an increase in coupling in the posterior subgenual cingulate cortex when experiencing self-blaming emotions (e.g. guilt, self-disgust) predicted whether people with MDD whose symptoms had subsided will develop another episode over the next year. These results are in keeping with the importance of excessive self-blame in MDD and have revealed the first fMRI biomarker of recurrence risk in MDD. Self-blame-related fMRI coupling therefore represents an excellent target for interventions to reduce the largely increased risk of recurrent episodes in people who have had one major depressive episode but are currently remitted (Eaton et al 2008).

[name], his team at the D'OR Institute for Research and Education in Rio de Janeiro (IDOR), in collaboration with [name] have provided the technical proof-of-concept that changes in self-blame-selective coupling on fMRI can be detected and fed back to the participants after a short temporal delay in a real-time fMRI setting (Moll et al., 2014). They have investigated whether coupling can be influenced through neurofeedback training (https://clinicaltrials.gov/ct2/show/NCT01920490?term=blame+rebalance&rank=1). This study was carried out at IDOR and is currently being prepared for publication (Principal Investigators: [name] and [name]). 24 patients with remitted MDD were double-blindly randomised to two different types of fMRI neurofeedback intervention delivered in

one session: one aimed at stabilising coupling between the anterior temporal lobe and the anterior subgenual cingulate region, the other aimed at increasing coupling between these regions. Both interventions were safe in that there was no increase in Beck Depression Inventory scores after neurofeedback. In fact, there was a trendwise decrease in BDI scores in the stabilisation group after a single session (t=-1.9, df=11, p=.08).

To our knowledge, there is no available neurofeedback intervention to reduce symptoms in patients with major depressive disorder (MDD) who have only insufficiently responded to standard treatment, one of the strongest clinical predictors of recurrence risk. Our novel approach of using fMRI neurofeedback aimed at brain connectivity whilst experiencing self-blaming feelings is highly promising, because it is aimed at the only functional anatomical change so far demonstrated to predict recurrence risk and residual symptoms in MDD. To date, there have been only two pilot studies using fMRI neurofeedback in MDD (n=8 vs. n=8 controls (1) and n=14 vs. n=7 controls (2)). These studies were promising in that patients' symptoms improved (1, 2). However, the studies were not randomised and investigated remission from the depressed state rather than early treatment resistance or recurrence risk. The clinical benefit of fMRI neurofeedback, however, is greater in those patients not sufficiently responding to standard treatment which is what the current study will investigate.

### **1.4. Background of methods used**

### **1.4.1. Magnetic Resonance Imaging**

Part of the participation in this study will involve a research scan with a 3T Magnetic Resonance Imaging (MRI) system, a common medical diagnostic tool that uses a strong magnetic field. Magnetic Resonance studies are accomplished by having the participant lie down on a bed that is slid into the 'bore' of the magnet. The 'bore' is a hollow cylinder that is 55-60 cm in diameter. A qualified person in an adjacent room performs the scan; audible communication is possible via intercom. In addition, the individual can be observed directly through a window between the two rooms. The individual can be removed immediately upon request or in case of emergency. MRI will be undertaken using modern scanners, which are less claustrophobic than older ones. During the scan, the participant will hear a thumping or buzzing sound. To reduce the level of noise and improve the comfort of the participants during the scanning, they will have ear plugs and ear padding to reduce the noise whilst also be positioned in the scanner as comfortable as possible. The duration of scanning varies from 45 minutes to 90 minutes and experience indicates that it is usually well tolerated by most participants.

#### **1.4.2. Functional MRI**

Functional Magnetic Resonance Imaging (fMRI) is used to monitor changes in signal intensity as a result of alteration of cerebral perfusion in response to cognitive stimulation. Significant technical advancements in the fast imaging techniques used in acquiring fMRI studies in the brain have been made allowing for the acquisition of multi-slice images for whole brain coverage in less than 2 seconds (Bandettini & Cox, 2000). Since neuronal activation (as compared to resting conditions) is accompanied by focal changes in cerebral blood flow, blood volume, blood oxygenation and metabolism, these changes can be measured and used to produce activation maps of cognitive, visual, motor and sensory tasks. Data will be analysed using the FRIEND neurofeedback software (primary outcome measure).

#### **1.4.3. Real-time fMRI Neurofeedback**

Technological advances in real-time functional MRI-based (fMRI) neurofeedback promise new treatment opportunities (Weiskopf, 2012; Sulzer et al., 2013). Using this technique, it has been demonstrated that people are quickly able to gain voluntary control over activity and connectivity of specific brain regions (Weiskopf, 2012; Sulzer et al., 2013). Real-time fMRI neurofeedback is a training method in which real time information about changes in neural activity is provided to the individual in order to facilitate learned self-regulation and to produce changes in brain function, cognition, or behaviour (Stoeckel et al., 2014). Studies have demonstrated promise of real-time fMRI neurofeedback in the treatment of various clinical conditions including chronic pain (deCharms et al., 2005), tinnitus (Haller et al., 2010), stroke (Sitaram et al., 2012), schizophrenia (Ruiz et al., 2013) and also current al., 2012). employ depression (Linden et We will software (FRIEND: http://fsl.fmrib.ox.ac.uk/fsl/fslwiki/OtherSoftware) specifically developed and validated for training brain coupling (Moll et al., 2014; Sato et al., 2013).

## 2. Methods

## 2.1. Study 1

## **2.1.1.** Specific aim and hypothesis

To determine whether fMRI neurofeedback is effective in the reduction of self-blame and depressive symptoms in insufficiently remitted major depression through the normalisation of self-blame-related neural coupling between the right superior ATL and the posterior SSCR. We hypothesise that patients undergoing active neurofeedback (ATL-subgenual - correlation decrease) will show reduced depressive symptoms, decreased self-blame and increased self-worth.

### 2.1.2. Trial design

Single-blind, parallel group, controlled and randomised clinical trial comparing 2 arms comprising of 3 treatment visits by measuring change between pre-treatment (Visit 1) and post-treatment assessments (Visit 5) of clinical outcomes:

- 1) 3 sessions of anterior temporal lobe-posterior subgenual cingulate correlation fMRI neurofeedback + psychological self-guided intervention to reduce self-blame and increase self-worth
- 2) 3 sessions of a solely psychological intervention to reduce self-blame and increase self-worth

In all conditions (active fMRI neurofeedback vs. solely psychological intervention), patients are instructed to differentiate and reappraise self-blame-related autobiographical memories using techniques modified from cognitive therapy and related approaches. Further, a novel experimental task will be applied investigating whether changes in social agency inferences underpin self-blaming biases in MDD.

## 2.1.3. Participants

60 MDD patients (n=24 in each group, plus an estimated 12 lost to follow-up) with insufficient remission of symptoms, patients continue to experience significant symptoms which have not responded to adequate treatment or patients who have not been amenable to adequate treatment. Antidepressant medication is no exclusion criterion, but patients need to be on a stable dose for at least 6 weeks without improvement which they are able to remain on for the duration of the study.

#### 2.1.4. Neurofeedback design

## (n=24; 3 active neurofeedback sessions over 3 weeks)

Scanning will be carried out on a General Electric 3T MRI system using sequences optimised for ventral and anterior temporal lobe signal (Zahn et al., 2009). The neurofeedback software (functional real-time interactive endogenous neuromodulation and decoding: FRIEND; Sato et al., 2013) has been previously validated for correlation feedback in patients with MDD.

- Before undergoing their first MRI scan, patients will come in for a clinical assessment and neurocognitive testing. Prior to their first neurofeedback session, patients will receive training materials via email and we may discuss these over the phone. Participants will be told that an upward and downward moving thermometer scale will appear during the neurofeedback scan related to their brain connections.
- In each of the 3 fMRI neurofeedback visits, the following procedure applies:  $1^{st}$  fMRI data acquisition  $\rightarrow 1^{st}$  neurofeedback  $\rightarrow 2^{nd}$  neurofeedback  $\rightarrow 2^{nd}$  fMRI data acquisition (which may be modified slightly whilst keeping the overall scanning time)
- The baseline consists of counting backwards from an arbitrary new number for every baseline trial (113, 108, 110, etc.)
- Autobiographical events recorded prior to scanning are played back to participant by using a cue word defined before (2 or more scenarios/events for each condition). The self-blame-evoking scenarios must involve the participant being the main agent of the scenario. The other-blaming scenarios must involve another person acting. (Only for data acquisition not for feedback.) Ratings on these events are obtained prior and after the scan to see whether there is a change in attribution. In the scanner, after each run the participant is asked over the intercom to rate on a scale from 1 to 7 how much he/she felt self-blame or other-blaming emotions, as well as the level of concentration (from 1 to 7). Additionally, in the feedback runs, participants will be asked how easy it was to use the thermometer during the self-blame and other-blame conditions (from 1 to 7) and how successful they felt at influencing the thermometer scale.
- The following neurofeedback instructions will be given and may be modified or amended: 'On the screen you will see a bar filled with colour that can reach different levels. The levels are calculated from your brain activity patterns with a delay of 6 seconds. Whilst in the scanner, keep thinking about the situation related to the cue word that will be displayed. Try to bring down the level to which the bar is filled with color to the bottom. If you get to the bottom try to keep it there. If the level rises, try to bring it down again.'
- During the neurofeedback sessions, the correlation between the ATL seed and the other posterior septal/subgenual region ROIs is used for feedback.

## 2.1.5. Summary of neurofeedback design

(Durations and block lengths may be modified, but this will not affect the overall scan time of 60 minutes including structural scans or 90 minutes in case of technical difficulties.)

- The session will have 4 runs:
  - Run 1: functional localizer, consisting of self-blame blocks, other-blame blocks and subtraction blocks to assess relative correlations for self-blame and other-blaming emotions
  - Run 2: neurofeedback training
  - Run 3: same as run 2
  - Run 4: same as run 1 to assess training effects on correlations for self-blame and other-blame
- The first 5 volumes of each emotional block will be discarded due to high correlations guided by decrease in time series after subtraction conditions. The moving correlation sliding window will be 10 volumes.
- Thermometer displayed:
  - Maximum= average previous 10 volumes (sigmoid function) + 1 SD
  - Minimum= average previous 10 volumes (sigmoid function) -1 SD

### 2.1.6. Trial flowchart

	Initial	Pre-Trial	Treatment	Treatment	Treatment	Post-Trial
	Patient	Assessment	Session	Session	Session	Assessment
	Contact	Visit 1	Visit 2	Visit 3	Visit 4	Visit 5
	(email	(day 0)	(1-13 days	(7-13 days	(7-13 days	(7-13 days
	and		after Visit	after Visit	after Visit	after last
	phone)		1)	2)	3)	treatment
	1 /		,	,		visit)
Oral informed	Х					
Introduction						
introduction	Х					
Assessment of						
Assessment of	Х	Х				
Writton						
written informed		v				
informed		Λ				
consent						
Clinical						
assessment &		37				
neuro-		X				Х
psychological						
tests						
fMRI			Х	Х	Х	
neurofeedback						
Psychological						
intervention			Х	Х	Х	
only						
Mood			x	x	x	
assessment			Δ	Δ	Δ	

## 2.1.7. Outcome measures

Primary outcome measure:

 Reduction of depressive symptoms between Visit 1 and 5 as assessed by the Beck Depressive Inventory (BDI-II). (Reduction of depressive symptoms between Visit 1 and the last treatment session as assessed by the Beck Depressive Inventory (BDI-II) for those who do not complete the study.)

Secondary outcome measures:

- 2) Reduction of depressive symptoms between Visit 1 and 5 as assessed by the Montgomery–Asberg Depression Rating Scale (MADRS) by a rater who is blinded to the treatment arm.
- 3) Reduction of self-rated depressive symptoms between Visit 1 and 5 as assessed by the Quick Inventory of Depressive Symptomatology (QIDS-SR 16).
- 4) Clinical Global Impression scale change between Visit 1 and 5 by a rater who is blinded to the treatment arm.
- 5) Withdrawal rates and adverse events after first treatment session.
- 6) Decrease in post vs. pre-training right ATL-SSCR correlation on fMRI (in neurofeedback arm).
- 7) Reductions in implicit self-blaming bias (self-contempt bias BIAT) between Visit 1 and 5.
- 8) Increase in Rosenberg Self Esteem Scale score between Visit 1 and Visit 5.

- 9) Positive Affect score increase and Negative Affect score decrease (PANAS scale) between Visit 1 and Visit 5.
- 10) Profile of Mood States (POMS) depression score change between Visit 1 and 5.
- 11) Self-blame ratings obtained prior to the first and after the last treatment session.
- 12) Reductions in agency-incongruent self-blame on short version of the value-related moral sentiment task between Visit 1 and 5.
- 13) Dysfunctional Attitudes Scale (prior & post mood induction if time permits) between Visit 1 and 5.
- 14) Self- & observer rated clinical global impression on Visit 5 for change since Visit 1.

We may have to drop some of the secondary outcome measures, depending on time constraints.

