- During the first session scheduled after screening for inclusion and exclusion criteria, standardised psychiatric assessments as well as self- and observer-report scales will be used to assess neuropsychiatric symptoms and to verify the clinical diagnosis. Clinical evaluation may take up to 2 hours and follows standard practice. Diagnostic interviews and scales will be limited to a maximum of 3 hours.
- In the fMRI neurofeedback condition, a separate session in a mock scanner may be arranged for people with no experience in MRI scanning to get familiar with the environment.
- At each visit, before and after the treatment session, patients will receive standardised scales to assess measures of individual differences on mood, cognition and personality. The researcher will alert the psychiatrist if the BDI-II suicidality item is rated above 0 and the subsequent Mini International Psychiatric Interview suicidality module results in a score indicating more than a low risk. The psychiatrist will then offer a consultation and decide with the patient whether to continue with the study.
- Participants will perform practice tasks prior to the MRI. This preparation may take up to 45 minutes. Scanning, including clinical, structural and functional scans will take 1 hour but may exceed that time in case of technical difficulties and if the patient/subject is willing to continue for up to 90 minutes, in very rare occasions 120 minutes. After the scanning participants perform computerised tests to correlate performance during the MRI scanning with performance outside of the scanner. This testing may take up to 1 hour.
- On two separately scheduled testing days (pre- and post-trial assessment, Visits 1 & 5), patients will perform neuropsychological tasks or give computerised self-report

ratings on mood, cognition and personality as well as on the stimuli delivered during MRI. These ratings may also be sent out as files to be completed by e-mail and returned by e-mail. Personally identifiable information will not be contained in the files exchanged by e-mail. Testing will be limited to 3 hours per day for patients and up to 4 hours per day for normal subjects, breaks will be planned depending on the needs of the participant.

- Following the post-trial assessment at Visit 5, the participant's GP will be notified about the results of relevant clinical measures.

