## 4. Diagnostic, Behavioural & Neuropsychological measures

From the following study measures we will select tests and measures which can be feasibly run within the stated time limits. We will therefore test the feasibility in a small group of patients to get a realistic time estimate and insure that patients and healthy controls are not overloaded with testing. All groups will have a baseline assessment of depressive symptoms (BDI-II, MADRS and QID-SR16) and experimental cognitive and emotional tests initially and as part of the post-trial assessment at Visit 5 (see outcome measures). Self-report scales (BDI-II and PANAS) will be carried out after each treatment session.

Clinical evaluation:

- Phone screening for exclusion and inclusion criteria of 15 to 20 minutes, major medical illnesses, substance abuse, axis-I disorders, pregnancy and MRI exclusion criteria, history of psychiatric and neurological treatments
- Non-structured clinical interview (all except healthy volunteers)
- Medical history including GP records if necessary (all)
- Day of menstrual cycle in women to use this as a covariate in the imaging analysis (in the high estrogen phase of the cycle brain activity is largely enhanced which adds variability to the data if not controlled for)
- Age at onset, episode duration, total illness duration
- MDD course: number of episodes, chronic, phasic, medication
- Beck Depression Inventory II (BDI-II; Beck & Brown, 1996)
- Montgomery-Asberg Depression Rating Scale (MADRS; Montgomery & Asberg, 1979)
- Global Social Functioning (GAF) Score (First et al., 2002)

- Psychiatric Family History Screen (Andreasen et al., 1977)
- AMDP Psychopathology Interview questions of depression items (translated from German; Faehndrich & Stieglitz, 1997; 2007)
- Mini International Neuropsychiatric Interview (MINI) suicidality Screen (Sheehan et al., 1998)
- Structured Clinical Diagnostic Interview (SCID)-I. Research Edition (First et al., 2002)
- Life Events Questionnaire (32 items). The scale aims to look at negative and positive life events, those occurring in the past and whether the respondent thinks they have a continuing influence and indicate whether the event was considered 'good', 'neutral' or 'bad'. Adapted from the List of Life Threatening Experiences (LTE; Brugha et al, 1985)
- Clinical Global Impression Scale (Busner & Targum, 2007)
- [LIFE] Longitudinal Interval Follow-up Interview (Keller et al., 1987)

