#### 8.2. Evaluation of risks

Risks from psychiatric assessments are minimal or non-existent. Some participants may find the interviews and tests tiring. To reduce this burden we have kept the number of clinical assessments to a minimum by using only relevant, widely used and validated assessment. MRI is safe when used on participants that are appropriately screened for the procedure (Shellock & Bierman, 1989). It is deemed that the risks to the participants in performing the neuropsychological, fMRI neurofeedback assessments in this protocol are minimal. Neurofeedback is reported to be a safe treatment, with only occasional reports of the occurrence of a possible side effect such as fatigue, headache, anxiety and difficulty falling asleep.

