## 9. Assessment of Safety

#### 9.1. Procedures for recording and reporting adverse events

An adverse event (AE) is any untoward medical occurrence in a patient or healthy volunteer, which does not necessarily have a causal relationship with the study procedures (i.e., neuropsychological, neuroimaging assessments, or neurofeedback training). The period of recording of AEs will last from the time that the subject signs the informed consent form to the last trial day according to the clinical trial protocol.

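### Secondary outcome 5, the only listed outcome for withdrawals and adverse events, starts after the first treatment session and so leaves out early withdrawals and events at first exposure

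*Protocol*

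**What the plan says.** Secondary outcome 5 reads "Withdrawal rates and adverse events after first treatment session", with the same wording in the synopsis of Study 1 and in section 2.1.7. No other item in the outcome list covers withdrawals or adverse events.

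Four other statements bear on it:

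- **Objective.** The primary objective in the synopsis begins "This study aims at testing clinical benefits and feasibility of a novel fMRI", so feasibility is part of it.
- **Sample.** The synopsis counts its 60 as "patients completing the first treatment visit after being randomised to one of the two treatment arms". Randomisation therefore comes before that visit is completed.
- **Recording of harms.** Section 9.1 says: "The period of recording of AEs will last from the time that the subject signs the informed consent form to the last trial day". The flowchart (2.1.6) puts written consent at Visit 1.
- **Arms.** Section 2.1.2 gives the control arm "3 sessions of a solely psychological intervention to reduce self-blame and increase self-worth", with no scanning. Section 3 adds: "In the fMRI neurofeedback condition, a separate session in a mock scanner may be arranged for people with no experience in MRI scanning".

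The first treatment session takes place at Visit 2, 1 to 13 days after Visit 1 (2.1.6).

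**The concern.** The protocol collects harms from consent and randomises before the first session ends, but the outcome that reports withdrawals and harms begins only once that session is over. A randomised patient who drops out before the session, or who cannot enter or finish the first scan and leaves, is not in the withdrawal rate. An adverse event during first exposure is not in the harms count.

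This matters because outcome 5 is the listed measure of whether patients stay in and what harms occur, in a pilot that has feasibility in its primary objective. Section 8.2 names a "possible side effect such as fatigue, headache, anxiety and difficulty falling asleep". Fatigue, headache or anxiety that arises in the scanner at the first of three sessions would fall outside the outcome as written.

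**Working it through.** **1. The plan's own figures.** Section 2.1.8 gives 24 per group plus 12 lost: 24 + 24 + 12 = 60, and 12/60 = 20%. At d = 1.06 and two-sided 0.05, the t-test with 24 per group has power 0.949 against the stated 95%, and 48/(1 − 0.20) = 60. These figures reproduce, and nothing below changes them.

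**2. What falls inside outcome 5 on the plain reading.**

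| Event | Recorded (9.1) | In outcome 5 |
|---|---|---|
| Withdrawal after randomisation, before the first session | not addressed by 9.1 | no |
| Withdrawal during the first session, for example an unfinished first scan | not addressed by 9.1 | no |
| Adverse event between consent and the first session | yes | no |
| Adverse event during the first session | yes | no |
| Adverse event or withdrawal later in Visit 2, after the session | adverse event: yes | yes |
| Anything from then to Visit 5 | adverse event: yes | yes |

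The boundary is the end of the session and not the end of the visit. Section 3 places scales before and after the session at each visit, and section 4 says: "Self-report scales (BDI-II and PANAS) will be carried out after each treatment session". Post-session time within Visit 2 is therefore covered.

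**3. Other readings of the phrase.**

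- If it means from the start of the first session onwards, events during that session are in. Withdrawals between randomisation and the session are still out.
- If it limits adverse events only, withdrawals have no stated start. Adverse events before and during the first session are still out.
- Only if both generous readings are combined does the gap shrink to adverse events before the first session.

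The synopsis definition of the 60 fits the plain reading best, since it also starts from completion of the first treatment visit. It does not settle the matter.

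**4. Illustration of size.** The number w who leave after randomisation but before completing the first treatment visit is not given. All values of w are assumptions, and w is used here as a stand-in for the withdrawals that outcome 5 misses. With 12 later losses among 60, outcome 5 reports 12/60 = 20.0% whatever w is. Among all randomised the rate is (12 + w)/(60 + w):

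| w | 0 | 2 | 4 | 6 | 8 | 12 |
|---|---|---|---|---|---|---|
| Rate | 20.0% | 22.6% | 25.0% | 27.3% | 29.4% | 33.3% |

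By arm, assume an equal split: 30 complete the visit and 6 are lost later in each arm. With k early losses the rate is (6 + k)/(30 + k): k = 0 gives 6/30 = 20.0%, k = 2 gives 8/32 = 25.0%, k = 6 gives 12/36 = 33.3%.

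| Early losses, neurofeedback v control | Rates | Difference | 95% half-width |
|---|---|---|---|
| 2 v 0 | 25.0% v 20.0% | 5.0 points | 20.7 |
| 6 v 0 | 33.3% v 20.0% | 13.3 points | 21.0 |
| 6 v 2 | 33.3% v 25.0% | 8.3 points | 21.5 |
| 2 v 2 | 25.0% v 25.0% | 0 points | 21.2 |

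The half-width is 1.96 × √[p₁(1 − p₁)/n₁ + p₂(1 − p₂)/n₂]. For 2 v 0 this is 1.96 × √(0.1875/32 + 0.16/30) = 0.207. Every difference lies within its half-width, so the point concerns complete reporting and not a test between arms.

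**The case against.** The case for leaving the line alone has four parts.

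- **No harms data are lost.** Adverse events are recorded from consent and all are reported to the Chief Investigator (9.1.2). This stands, and it limits the point to the outcome definition.
- **Attrition is addressed elsewhere.** Section 2.1.9 promises to analyse what was collected on patients lost to follow-up and to include their partial data. This softens the gap but defines no withdrawal rate from randomisation. Tabulation detail may belong in an analysis plan that is not shown, but here the protocol itself fixes the starting point, twice.
- **The choice is coherent.** It matches the sample definition and resembles an exposed-patient set. That justifies keeping the count as a second line. It does not justify having it as the only line, because a patient who fails the first scan has been exposed and is still left out.
- **The wording is terse.** Other readings are possible, as shown above, and the plain reading should not be presented as certain.

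A reader might also infer that the rule makes neurofeedback look better tolerated than it is. The protocol does not support that. Scan-related losses can arise only in that arm, but blinding is only partial (2.1.9), so control patients may leave on learning that they will not get neurofeedback. A stop triggered by the scales given before the Visit 2 session could occur in either arm.

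**Conclusion.** The point holds in a limited form. As worded, outcome 5 omits withdrawals from randomisation to the end of the first treatment session, and adverse events before or during that session. One kind of omitted loss, failure to enter or finish the first scan, can arise in one arm only. The net direction of bias is unknown.

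The size cannot be derived from the protocol. The gap of 0 to 13 points in the pooled withdrawal rate rests on assumed early losses of 0 to 12. A reader might instead measure the gap by the time from Visit 1 to Visit 2, which is 1/(1 + 39) = 2.5% to 13/(13 + 21) = 38% of the time from Visit 1 to Visit 5. That is not a sound measure: the time of randomisation is not stated, and no treatment session falls in that interval.

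The definition of the primary outcome, the power and the sample size are untouched. The change is still worth making, because the rule bears on feasibility and harms and costs little to correct.

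**What to change.** In section 2.1.7 and the synopsis, reword outcome 5 as: *Withdrawals from randomisation to Visit 5, and adverse events from randomisation (including during the first treatment session) to Visit 5, by arm, for all randomised patients.* Give the count after the first treatment session as a second line. Report the number randomised per arm beside the 60 who complete the first treatment visit. Adverse events between consent and randomisation can be listed separately, without comparison by arm.

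The cost is one reworded line in two places. Adverse events are already recorded over the whole period, and withdrawals of randomised patients should be known from the allocation and visit records, so no visits or patients are added. The downside is that the withdrawal rate may look less favourable and will include patients who left before any exposure. The second line separates them out.
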